1.1 Study design

[figure not shown]
This is a multicenter, prospective, phase II, single-arm, open-label study to assess the efficacy and safety of crizanlizumab in SCD (Sickle Cell Disease) subjects with priapism.

A total of approximately 36 male subjects aged ≥ 12 years, who meet all of the inclusion criteria and none of the exclusion criteria will be eligible for the study. Subjects with ≥ 4 priapic events during the 14 week pre-screening period and having at least 3 priapic events during the 12 week screening period with at least 1 event occurring within 4- weeks prior to the first treatment, will be included in the study.

The baseline period is defined as the 12 weeks screening period. Eligible subjects will be treated with crizanlizumab at a dose of 5.0 mg/kg. From the first screening visit until the end of follow-up, the total study duration will be 79-weeks (including 12 weeks of screening, 52 weeks of treatment and 15 weeks of follow-up period). The primary analysis of the study will be conducted by 26 weeks to assess efficacy of crizanlizumab in those subject population, who have completed 26 weeks of treatment. The secondary [REDACTED] endpoints will be assessed by 26 weeks and/or 52 weeks. Subjects will be followed for safety for up to 105 days (15 weeks) after the last dosing if applicable. Subjects who will receive commercially approved crizanlizumab approximately 4 weeks after their last dose of study treatment, do not need to

complete the 105-day follow-up. The safety follow-up of these subjects will be at the End of Treatment (EOT) visit. All other subjects are required to complete the 105-day follow-up visit.

Figure 1-1 Study design

1.2 Study objectives, endpoints and estimands

Table 1-1 Study Objectives and endpoints

Primary Objective	Endpoint for primary objective
To evaluate the clinical efficacy of crizanlizumab in SCD-related priapism	Percent reduction from baseline period in priapic events (priapism defined as unwanted, or painful erection lasting at least 60 min self-reported) by 26 weeks
Secondary Objectives	Endpoints for secondary objectives
To evaluate the clinical efficacy of crizanlizumab in SCD-related priapism	Rate of priapic events by 26 and 52 weeks
To evaluate the clinical efficacy of crizanlizumab in SCD-related acute priapism	Percent reduction from baseline in acute priapic events (defined as an unwanted or painful erection lasting at least 4 hours and mandates a visit to ER) by 26 weeks and 52 weeks
To evaluate the clinical efficacy of crizanlizumab for uncomplicated vaso-occlusive crisis (VOC) (defined as an acute event of pain with no known cause for pain other than a vaso-occlusive event; and requiring treatment with a parenteral or oral opioids or other parenteral analgesic; but is NOT classified as an acute chest syndrome, hepatic sequestration, splenic sequestration or priapism and these events will not be adjudicated)	Rate of uncomplicated VOC events (including both healthcare visit and self-reported) by 26 and 52 weeks
To evaluate the clinical efficacy of crizanlizumab in complicated VOCs (acute chest syndrome, hepatic sequestration, splenic sequestration, and acute priapism)	Rate of complicated crisis (recorded by healthcare visit) by 26 and 52 weeks
To assess the safety and tolerability of crizanlizumab	Number, seriousness, severity, and causality assessments of treatment emergent adverse

events and other safety data as considered appropriate by 52 weeks (Safety assessments will consist of monitoring and recording all adverse events, based on Common Terminology Criteria for Adverse events (CTCAE) V5.0.

It will also include regular monitoring of laboratory testing of hematology, serum chemistry, and urinalysis, measurement of vital signs, and physical examination.)

1.2.1 Primary estimand(s)

The estimand is the precise description of the treatment effect and reflects strategies to address events occurring during trial conduct which could impact the interpretation of the trial results (e.g. premature discontinuation of treatment).

The primary clinical question of interest is: What is the effect of crizanlizumab on reduction from baseline period in priapic events, by week 26?

The primary estimand is described by the following attributes:

1. Population: Sickle Cell Disease patients with priapism.
2. Endpoint: Percent reduction from baseline period in priapic events (priapism defined as unwanted, or painful erection lasting at least 60 min self-reported) by 26 weeks
3. Treatment of interest: Investigational drug will be a crizanlizumab solution provided every 4 weeks with an additional loading dose 2 weeks after the first dosing.
4. List of intercurrent events:
 - a) Treatment discontinuation.
 - b) Initiation or discontinuation of HU/HC or l-Glutamine (or other therapies to treat SCD and or to prevent/reduce VOCs such as voxelotor and erythropoietin) or of prophylactic treatment for priapism.
 - c) Intake of analgesic (including opioids) or ad hoc transfusions administered temporarily.

5. The summary measure: Median percentage change from baseline period in priapic events (priapism defined as unwanted, or painful erection lasting at least 60 min self-reported) by 26 weeks

Handling of intercurrent events is discussed in [Section 2.5.3](#)

1.2.2 Secondary estimand(s)

Not applicable

2 Statistical methods

2.1 Data analysis general information

The data will be analyzed by Novartis and/or a designated contract research organization (CRO) (if applicable). It is planned that the data from all centers that participate in this protocol will be used for analysis. Analysis datasets and statistical outputs will be produced using the most recent SAS® Version 9.4 (SAS Institute Inc., Cary, NC, USA), and stored in Novartis global programming & statistical environment (GPS).

General analysis conventions

Descriptive statistics for continuous variables will include number of subjects (n), mean, standard deviation (SD), minimum, lower quartile (Q1), median, upper quartile (Q3), maximum. Summary statistics for discrete variables will be presented in the number and percent of subjects in each category. Summary statistics will also be presented graphically wherever applicable.

If not otherwise specified, p-values and confidence interval (CI) will be presented as two-sided. Unless otherwise stated, the default level of significance will be set to 5%.

For categorical data, percentages will be rounded up to one decimal place. For continuous data, mean, and median will be rounded up to one additional decimal place compared to the original data. Standard deviation will be rounded up to two additional decimal places. Minimum and maximum will be displayed with the same accuracy as in the original data. Wherever changes from baseline will be used, change will be calculated as “post-baseline value – baseline value”. The number of decimal places for the “change from baseline” variables will be the same as for the original measurement.

The analysis will be conducted on all subjects' data at Week 26 and at the time, the trial ends (Week 52).

Unscheduled assessments

The following points summarize the rules for unscheduled assessments:

- All unscheduled assessments at the baseline before the first dose should be included for consideration when calculating the baseline value.
- In summary tables by visit, unscheduled assessments should not be included unless they qualify as baseline.

- In shift and abnormality tables, all unscheduled assessments are included.

Unscheduled assessments will be reported along with the scheduled assessments in the listings.

Data included in analysis

All statistical analyses will be performed using all data collected in the database up to the data cut-off date. All data with an assessment date or event start date (e.g., vital sign assessment date or start date of an adverse event) prior to or on the cut-off date will be included in the analysis. Any data collected beyond the cut-off date will not be included in the analysis and will not be used for any derivations at the time of the primary analysis.

All events with start date before or on the cut-off date and end date after the cut-off date will be reported as 'ongoing'. The same rule will be applied to events starting before or on the cutoff date and not having documented end date. This approach applies, in particular, to adverse event and concomitant medication reports. For these events, the end date will not be imputed and therefore will not appear in the listings.

For the final analysis, all data collected will be used, without notion of cut-off date.

2.1.1 General definitions

Study treatment: Study treatment refers to Crizanlizumab (SEG101) 5.0 mg/kg provided by IV infusion.

Study treatment start and end date: Study treatment start date is defined as the first date when a non-zero dose of study drug is administered and recorded on the Drug Administration Record (DAR) CRF page. Similarly, study drug end date is defined as the last date when a non-zero dose of study drug is administered and recorded on the DAR CRF page of the core study.

Baseline: Baseline period is defined as 12 weeks screening period prior to the first infusion of crizanlizumab 5 mg/kg at Week 1 Day 1.

- For the analysis purpose, in the tables and figures, baseline is considered from Day -91 to one day prior to dosing. Similarly, for "by week 26 analysis" from the first dose date to one day prior to Week 27 Day 1 visit date and for "by week 52 analysis" from the first dose date to one day prior to Week 53 Day 1 visit date will be considered.
- For subjects missing "Week 27 Day 1" visit or "Week 53 Day 1" visit, the scheduled visit day will be considered for cut-off.
- For listings, all available data will be considered.

For safety evaluations, the last available assessment on or before the date of start of study treatment is taken as "baseline" assessment. In case time of assessment and time of treatment start is captured, the last available assessment before the treatment start date/time is used for baseline.

For safety parameters (e.g. ECGs), where study requires multiple replicates per time point, the average of these measurements will be calculated for baseline (if not already available in the database).

In cases where multiple measurements meet the baseline definition, with no further flag or label that can identify the chronological order, then the following rule should be applied: If values are from central and local laboratories, the value from central assessment should be considered as baseline. If multiple values are from the same laboratory (local or central) or collected for ECGs or vital signs, then the last entry should be considered as baseline.

If subjects have no value as defined above, the baseline result will be missing.

Post baseline: Any measurements taken after baseline will be considered as post-baseline measurements.

Change from baseline: Post baseline value – baseline value

Percent change from baseline: (Post baseline value – baseline value) *100/ Baseline value;
(relative change from baseline).

Reduction: The negative change from baseline.

Study day: The study day, describes the day of the event or assessment date, relative to the start of study treatment. Study Day 1 for all assessments is taken to be the start of study treatment.

The study day is defined as:

- The date of the event (visit date, onset date of an event, assessment date etc.) - Start of study treatment + 1, if event is on or after the start of study treatment;
- The date of the event (visit date, onset date of an event, assessment date etc.) - Start of study treatment, if event precedes the start of study treatment.

The study day will be displayed in the data listings. If an event starts before start of study treatment, the study day displayed in the listing will be negative.

On-treatment assessment/event:

For AE reporting the overall observation period will be divided into three mutually exclusive segments:

1. Pre-treatment period: from day of subject's informed consent to the day before first dose of study medication
2. On-treatment period: from day of first dose of study medication to 105 days after last dose of study medication (or until EOT date for subjects continuing crizanlizumab after their EOT via commercial supply)
3. Post-treatment period: starting at Day 106 after last dose of study medication (or after EOT date for subjects continuing crizanlizumab after their EOT via commercial supply or a post-trial access program)

Note: If dates are incomplete in a way that clear assignment to pre-, on-, post-treatment period cannot be made, then the respective data will be assigned to the on-treatment period.

Safety summaries (tables, figures) include only data from the on-treatment period, unless specified otherwise, with the exception of baseline data which will also be summarized where appropriate (e.g., change from baseline summaries).

Time unit: A year length is defined as 365.25 days. A month length is 30.4375 days (365.25/12). If duration is reported in months, duration in days will be divided by 30.4375. If duration is reported in years, duration in days will be divided by 365.25.

Visit windows

Visit-windows will be applied for vital signs, laboratory and PRO assessments.

Visit-windows will be used for the data that is summarized by visit; they are based on the study evaluation schedule and comprise a set of days around the nominal visit day. For any assessment, there are the protocol defined scheduled visits around which visit windows were created to cover the complete range of days within the study. The visit windows are shown in Table 2-1. These apply to measurements taken at every visit.

When visit windows are used, all visits will be re-aligned, i.e., they will be mapped into one of the visit windows (e.g., if the Week 4 visit of a subject is delayed and occurs on Day 46 instead of on Day 29, say, it will be re-aligned to visit window Week 8). In the case of major deviations from the visit schedule, or due to unscheduled visits, several assessments of a subject may fall in a particular visit window (either scheduled or unscheduled). Statistical approaches to handle multiple assessments in a given visit window are specified below.

Table 2-1 Assessment windows for scheduled visits

Analysis Visit	Week (k)	Scheduled Day/ Target day [d=(k-1)*7+1]	Visit Window (in study days)
Baseline	BSL		-91 days to Day -1*
Week 1 Day 1	1	1	Day 1-7
Week 3 Day 1	3	15	Day 8-29
Week 7 Day 1	7	43	Day 30-57
Week 11 Day 1	11	71	Day 58-85
Week 15 Day 1	15	99	Day 86-113
Week 19 Day 1	19	127	Day 114-141
Week 23 Day 1	23	155	Day 142-169
Week 27 Day 1	27	183	Day 170-197
Week 31 Day 1	31	211	Day 198-225
Week 35 Day 1	35	239	Day 226-253
Week 39 Day 1	39	267	Day 254-281
Week 43 Day 1	43	295	Day 282-309
Week 47 Day 1	47	323	Day 310-337
Week 51 Day 1	51	351	Day 338-358
EoT	53	365	Day 359-371**

*Baseline measurement prior to first infusion of study drug.

**Based on medical judgement and data, upper limit of EoT will be extended upto maximum value day 447.

Laboratory assessments will be taken from Screening Visit 3 as per the protocol and the window does not include pre-screening period. Thus, window for laboratory assessments will be Day - 28 to Day -1.

Multiple assessments within visit windows

In order to summarize laboratory assessments over time (including unscheduled visits), the assessments will be time slotted. The following general rule will be applied:

- If more than one assessment is done within the same time window, the assessment performed closest to the target date will be used.
- If 2 assessments within a time window are equidistant from the target date, then the earlier of the 2 assessments will be used.
- If multiple assessments are on the same date then the worst case will be used (minimum or maximum depending of the parameter direction).

Data from all assessments (scheduled and unscheduled), including multiple assessments, will be listed.

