## 8 Visit schedule and assessments

[Table 8-1](#) lists all of the assessments and indicates with an “X”, the visits when they are performed. All data obtained from these assessments must be supported in the subject’s source documentation.

Subjects should be seen for all visits/assessments as outlined in the assessment schedule ([Table 8-1](#)) or as close to the designated day/time as possible. Missed or rescheduled visits should not lead to automatic discontinuation. Subjects who prematurely discontinue the study for any reason should be scheduled for a visit as soon as possible, at which time all of the assessments listed for the final visit will be performed. At this final visit, all dispensed investigational product should be reconciled, and the AE and concomitant medications recorded on the CRF.

If the subject cannot or is unwilling to attend any visit(s), the site staff should maintain regular telephone contact with the subject, or with a person pre-designated by the subject. This telephone contact should preferably be done according to the study visit schedule.

The table indicates which assessments produce data to be entered into the clinical database (D) or remain in source documents only (S) (“Category” column).

Allowed visit windows are specified as follows:

- Screening assessments must occur within 84 days (12 weeks)  $\pm$  7 days prior to the enrollment as per [Table 8-1](#).
- For all screening visits a general  $\pm$  7 day visit window is allowed
- A  $\pm$  7 day visit window is allowed at Week 1 Day 1 (calculated from day of consent)
- A  $\pm$  3 day visit window is permitted on assessments at Week 3 Day 1.
- For all other dosing visits a general  $\pm$  7 day visit window is permitted on assessments
- A  $\pm$  7 day visit window for the end of treatment phase (last infusion + 2 weeks) is allowed.
- A + 7 day visit window for the end of the safety follow-up phase (last infusion + 105 days) is allowed.

Every effort should be made to follow the schedule outlined in [Table 8-1](#).

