c Certain adverse events reported in the AE/SAE eCRF as Infusion Related Reactions will require the IRR eCRF to be completed.

d Local sampling for platelet assessment will be performed throughout the trial for all subjects.

e The date, number, and duration of the priapic events in the 14-week period prior to consenting will be captured in a separate CRF.

f Subjects who will receive commercially approved crizanlizumab approximately 4 weeks after their last dose of study treatment, do not need to complete the 105-day follow-up.

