2.5.2 Statistical hypothesis, model, and method of analysis

It is expected that crizanlizumab treatment reduces priapic events by at least 25% in SCD subjects with priapism.

Demonstration of significant percent reduction from baseline in priapic events will be evaluated using following hypothesis:

$H_0: p < 0.25$, where p is the percent reduction in priapic events by 26 weeks.

$H_1: p \geq 0.25$, where p is the percent reduction in priapic events by 26 weeks.

If the above null hypothesis is rejected, significant reduction in priapic events will be demonstrated statistically.

Assuming uniformity in the occurrence of priapic events before exposure to crizanlizumab treatment, baseline will be adjusted for 26 weeks for analysis purpose.

Baseline (adjusted for 26 weeks): Number of priapic events in 12 weeks screening period * (26/12) and percentage change from baseline = (Post baseline value –Baseline (adjusted to 26 weeks) value) * 100 / Baseline (adjusted to 26 weeks) value.

Percentage reduction from baseline is the negative percentage change from baseline.

Percent reduction from baseline in priapic events will be tested using a non-parametric test (i.e., Wilcoxon's Sign Rank test) and p-value will be reported. The study would be declared a success, if percentage reduction in events is $\geq 25\%$ and $p < 0.05$ is obtained from Wilcoxon's Sign Rank test.

Hodges-Lehmann estimate of median percent reduction in priapic events will also be reported, along with corresponding 95% confidence intervals.

Number of priapic events will be summarized at baseline (adjusted for 26 weeks) and by Week 26, and percent reduction from adjusted baseline by Week 26 will be summarized by n, mean, standard deviation (SD), lower quartile (Q1), median, upper quartile (Q3), minimum and maximum.

Graphical representation of percentage reduction, through box plot or bar graph or waterfall plot, will be performed as appropriate by 26 weeks.

In addition, subgroup analysis of the primary endpoint will be performed based on the number of priapic events categories (i.e. <7, 7 - 13, 14 - 21, \geq 22) at baseline (12 weeks) and baseline (adjusted for 26 weeks). Additional analyses of the primary endpoint will also be performed for the subgroups of subjects with stuttering and acute priapism. Summary statistics for percentage reduction by 26 weeks will be presented for each subgroup.

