2.5.6 Supportive analyses

The supportive analyses described below will be performed on all FAS patients who have completed 26 weeks on treatment. Missing values will be imputed as stated in [Section 2.5.4](#)

Supportive analysis 1:

Annualized priapic Events Rate: The annualized rate of priapic events is defined as the total number of priapic events for a subject occurring from the date of initial infusion to the last contact date of the Treatment Phase of the study \times 365.25 divided by the number of days during that same time period. This calculation accounts for early dropouts or lost to follow-up by extrapolating the priapism events rate of every subject to 1 year.

Supportive analysis 2:

Percent reduction from baseline in priapic events will also be assessed by Week 52. Assuming uniformity in the occurrence of priapic events before exposure to crizanlizumab treatment, baseline will be adjusted for 52 weeks for analysis purpose.

Baseline (adjusted for 52 weeks): Number of priapic events in 12 weeks screening period \times (52/12) and percentage change from baseline = (Post baseline value – Baseline (adjusted to 52 weeks) value) \times 100 / Baseline (adjusted to 52 weeks) value.

Percentage reduction from baseline is the negative percentage change from baseline.

Supportive analysis 3:

The total number of priapic episodes in the screening period (12 weeks baseline) will be compared to the total number of priapic episodes occurring in the first 12 weeks on treatment (0-12 weeks) using a nonparametric test (i.e. Wilcoxon's Sign Rank test). Additionally, a similar analysis will be performed to compare to the total number of priapic episodes occurring in the last 12 weeks on treatment (15-26 weeks). For the analysis purpose, for 0-12 weeks: Day 1 to Day 84 and for 15-26 weeks: Day 105 to Day 182 will be used.

Supportive analysis 4:

Number of priapic events will be summarized in the screening period (12 weeks baseline), in first 12 weeks on treatment (0-12 weeks), and in the last 12 weeks on treatment (15-26 weeks) and percent reduction from baseline will also be summarized. For the analysis purpose, for 0-12 weeks: Day 1 to Day 84 and for 15-26 weeks: Day 105 to Day 182 will be used.

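### Baseline priapic events are counted over up to 91 days but scaled by a fixed 26/12 (or 52/12) that is right only for 84 days; the direction of the trial-level error is unknown

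*SAP*

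**What the plan says.** SAP 2.1.1 first defines baseline as the 12-week screening period before the first infusion. It then gives the rule used for analysis: "For the analysis purpose, in the tables and figures, baseline is considered from Day -91 to one day prior to dosing". SAP 2.5.2 obtains the 26-week baseline as "Number of priapic events in 12 weeks screening period * (26/12"), and percent reduction is computed from that figure. For Week 52, supportive analysis 2 in SAP 2.5.6 says "baseline will be adjusted for 52 weeks for analysis purpose", with the factor 52/12.

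Screening length is allowed to vary. Protocol section 8 gives a plus or minus "7 day visit window is allowed at Week 1 Day 1 (calculated from day of consent"). It also allows plus or minus 7 days at later infusion visits, in the item that begins "For all other dosing visits a general".

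On treatment, SAP 2.1.1 counts events "from the first dose date to one day prior to Week 27 Day 1 visit date". If that visit was missed, "the scheduled visit day will be considered for cut-off". The percent-change formula has no term for the length of either window.

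Elsewhere the SAP does handle time. The on-treatment annualized rates (SAP 2.5.6, supportive analysis 1, and SAP 2.6.2) divide by actual days. Supportive analyses 3 and 4 use fixed study days: Day 1 to 84 for the first 12 weeks and Day 105 to 182 for weeks 15 to 26.

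**The concern.** This is a single-arm before-and-after trial. The primary endpoint is a ratio of two event counts, judged against a 25% threshold, and there is no control arm in which an error in observation time could cancel. If the two counts cover different lengths of time and the scaling ignores this, scheduling is read as drug effect. A subject screened for longer than 84 days looks improved before any drug effect. A subject screened for less, or with a late Week 27 visit, has some benefit hidden. The outer limit of Day -91 fits the permitted 84 plus 7 days, but the multiplier still assumes 84.

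**Working it through.** **Inputs.** Baseline window: Day -91 to Day -1, which is 91 days because the SAP's study-day definition has no Day 0. Screening length B: 84 ± 7, so 77 to 91 days (Protocol 8). Scheduled Week 27 Day 1: Day 183 (SAP Table 2-1). With ± 7 days the visit falls on Day 176 to 190, so the on-treatment count covers F = 175 to 189 days. Success rule: reduction of at least 25% and p < 0.05 (SAP 2.5.2).

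**The plan's own factors.** 26/12 = 182/84 = 2.1667 and 52/12 = 364/84 = 4.3333. Each is exact when B = 84 and only then.

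**Per subject.** With true rate ratio RR (1 means no effect):

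apparent reduction = 1 − RR × F / (B × 26/12)

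With RR = 1 (a negative value is an apparent increase):

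| B (days) | F = 175 | F = 182 | F = 189 |
|---|---|---|---|
| 91 | 11.24% | 7.69% | 4.14% |
| 84 | 3.85% | 0% | −3.85% |
| 77 | −4.90% | −9.09% | −13.29% |

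The middle column isolates the baseline error: 1 − 84/91 = 7.7% and 84/77 − 1 = 9.1%. The middle row isolates the Week 27 error: 7/182 = 3.85%. At F = 182, the true reduction that reads as 25% is 1 − 0.75 × B/84, which is 18.75% for B = 91 and 31.25% for B = 77. The 52/12 factor gives the same 7.7% and 9.1% at Week 52 when F = 364.

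**Trial level (illustrative).** The documents give no screening lengths, so these are assumed. Set-up: 34 subjects; Poisson counts at one common rate; eligibility of at least 4 events in the 98 days before screening, at least 3 in screening and at least 1 in the last 28 days; 182 treatment days; two-sided 5% signed-rank test in the favourable direction; a true 25% reduction tested against 25%. The nominal rate is 2.5%. The sample-size section gives a mean of 10.0 by 26 weeks; 10 per 12 weeks is a second assumption to show the range.

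| Screening lengths | 10 per 26 weeks, fixed v exact scaling | 10 per 12 weeks, fixed v exact scaling |
|---|---|---|
| all 91 days (worst case) | about 34% v 11% | about 9% v 0.6% |
| even over 84–91 | about 25% v 14% | about 2.8% v 0.6% |
| even over 77–91 | about 17% v 17% | not tabulated |
| all 77 days | about 6% v 28% | not tabulated |

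Repeat runs agree to within two or three percentage points. The window accounts only for the difference within each pair. What remains under exact scaling comes from eligibility selection and the skewed percent scale.

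**Supportive analyses 3 and 4.** Day 105 to 182 is 182 − 105 + 1 = 78 days. The target-day formula in SAP Table 2-1 puts Week 15 Day 1 at (15 − 1) × 7 + 1 = Day 99, and 182 − 99 + 1 = 84 days. The count is therefore short by 1 − 78/84 = 7.1% for every subject, whatever the baseline length. Set unscaled against a 91-day baseline, the built-in reduction is 1 − 78/91 = 14.3%.

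**The case against.** The permitted screening range is symmetric about 84 days, both SAP sections speak of 12 weeks, and the plan states its assumption that events occur uniformly before treatment. On that view 26/12 is right on average and Day -91 is merely the outer edge of the window. This stands as far as the average goes: if lengths centre on 84 there is no net inflation. It does not remove the per-subject error. If 12 weeks is read as a strict 84 days, SAP 2.1.1 and 2.5.2 contradict each other.

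The Week 27 cut-off follows the endpoint definition in Protocol 12.4.1 and SAP 2.5.1, which runs to the pre-infusion visit. Its effect is small and symmetric, and the scheduled day is a sensible default for a missed visit. All of that stands, and it is why this part is secondary. The annualized rates do use actual days on treatment, but they do not correct the primary endpoint.

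A reader might infer that every subject has a 91-day baseline, so that the reduction is inflated systematically. That would follow if events before consent were counted. The documents point the other way: baseline is defined as the screening period, and Protocol Table 8-1 says "The date, number, and duration of the priapic events in the 14-week period prior to consenting will be captured in a separate CRF". SAP 2.1.1 should nevertheless give the start day, because for shorter screening Day -91 falls before consent.

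**Conclusion.** The scaling is wrong as written for any subject whose baseline is not 84 days, and nothing else in the plan corrects the primary endpoint. The per-subject error runs from a spurious 7.7% reduction to a spurious 9.1% increase. With both windows at their limits it runs from an 11.2% reduction to a 13.3% increase. These figures follow from the stated windows and a constant event rate.

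Neither the direction nor the size of the trial-level error can be stated. A reader might take the 34% as the trial's false-positive rate. The documents do not support that: it needs all 34 subjects dosed on the last permitted day, it falls to about 9% at the higher event rate, and 11 of the 34 points remain under exact scaling. The Day 105 slip is separate and certain, but confined to two supportive analyses. The whole point should be fixed because the remedy is simple and a pre-specified primary endpoint should not depend on when visits happened to be booked.

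**What to change.** 1. In SAP 2.1.1, count baseline events from the later of the consent date and Day -91 through Day -1, and let B be the number of days in that same window. Replace 26/12 by 182/B in SAP 2.5.2 and 52/12 by 364/B in SAP 2.5.6.
2. For the Week 26 and Week 52 percent reductions, end the count at Day 182 and Day 364 for every subject, which also makes the missed-visit rule unnecessary. Leave time lost to intercurrent events or dropout to the planned Poisson imputation; do not extrapolate it. Record the change in SAP section 4, because it departs from the pre-infusion Week 27 Day 1 wording in Protocol 12.4.1 and SAP 2.5.1.
3. In supportive analyses 3 and 4, change Day 105 to Day 99 and scale the baseline count by 84/B.

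The cost is a few lines of SAP text and programming, plus one documented change from the protocol wording. Consent, dosing and event dates are already collected. The change removes the window error only; it does not address eligibility selection or the skew of the percent scale.
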